7.2.5.3. Exploratory Endpoints

Descriptive summaries will be provided for the exploratory endpoints (Section 2), and additional analyses may be conducted. Details will be described in the SAP.

7.2.6. Pharmacodynamic Analysis

The PD endpoint is serum TTR. Summary tables will be provided for observed values, change and percentage change from baseline for each scheduled time point. In addition, the maximum and mean percentage reduction over 12 months will be summarized.

7.2.7. Pharmacokinetic Analysis

7.2.7.1. Pharmacokinetic Analysis

Plasma concentrations of ALN-18328, DLin-MC3-DMA, and PEG₂₀₀₀-C-DMG will be obtained using a model-independent method. PK exposure parameters will include: maximum plasma concentration at the end of infusion (C_{max}), 30-minute post-infusion concentration ($C_{p(30min)}$), and

pre-infusion concentration (C_{\min}). In addition, the steady-state C_{\max} ($C_{\max,ss}$), steady-state $C_{p(30\text{min})}$ ($C_{p,ss(30\text{min})}$), and steady-state C_{\min} ($C_{\min,ss}$) will be calculated as the average of the respective values at Week 24, Week 36, and Month 12.

The PK exposure parameters will be summarized by visit, and the steady-state PK parameters will be summarized.

7.2.7.2. Exposure-Response Analysis

Mean and maximum percent TTR reduction from baseline will be summarized by quartiles of the steady state PK parameters for all 3 analytes. Change from baseline at Month 12 in clinical efficacy parameters may also be summarized by quartiles of the steady-state PK parameters for all 3 analytes.

PK exposure will be summarized by mortality status. In addition, the incidence of AEs and SAEs will be summarized by quartiles of the steady-state PK parameters for all 3 analytes.

7.2.7.3. Population PK, PK/PD, and Disease Progression Modelling Analysis

Population PK, PK/PD, and disease progression modelling analyses may be performed, if appropriate. If performed, the analyses would be conducted according to a pre-specified analysis plan and reported separately.

7.2.8. Safety Analyses

The primary parameter is the frequency of treatment-emergent AEs (hereafter referred to simply as AEs). Safety parameters also include vital signs, ECGs, clinical laboratory assessments and physical examinations. The extent of exposure will be summarized.

Prior and concomitant medications will be coded using the World Health Organization Drug Dictionary. Results will be tabulated by the Anatomical Therapeutic Chemical classification system and Preferred Term (PT).

Adverse events will be classified according to the Medical Dictionary for Regulatory Activities (MedDRA) System Organ Class and Preferred Term. The frequency and percentage of patients experiencing AEs, SAEs, related AEs, and AEs leading to discontinuation will be summarized by System Organ Class (SOC) and PT. By patient listings will be provided for deaths, SAEs, and AEs leading to discontinuation.

Descriptive statistics will be provided for clinical laboratory data, ECG, and vital signs data, summarizing the observed values and change from baseline over time. Laboratory shift tables from baseline at the worst post-baseline values will be presented. Abnormal physical examination findings and 12-lead ECG data will be presented in by-patient listings.

Other safety summaries will be presented as appropriate. Further details will be specified in the SAP.

7.2.9. Immunogenicity Analyses

The frequency and percentage of patients with confirmed positive ADA assay at any time during study as well as at each scheduled visit will be summarized. The titer results for patients with

confirmed positive ADA results will be summarized. The impact of ADA on PK, PD, efficacy and safety endpoints will be explored. Details will be described in the SAP.

7.2.10. Sample Size Re-assessment

Patients who are tafamidis-naïve at baseline may opt to begin tafamidis treatment (ie, “tafamidis drop-in”) during the double-blind period, which could result in a loss of statistical power. An interim assessment may be performed to assess the impact of tafamidis drop-in on the power and the potential need to increase the sample size. The interim assessment, if conducted, would examine the overall tafamidis drop-in rate in a blinded manner (ie, a non-comparative assessment of the drop-in rate); therefore, no impact on the type I error is expected and no multiplicity adjustment will be made. A detailed sample size re-estimation plan will be outlined in a separate document prior to implementation.

7.2.11. Optional Additional Research

Optional additional research may be conducted in the future on the biological samples and/or data collected during the study in accordance with the strict terms of the informed consent form (see Section 4.3.2).

8. STUDY ADMINISTRATION

8.1. Ethical and Regulatory Considerations

This study will be conducted in accordance with the protocol, all applicable regulatory requirements, and the current guidelines of Good Clinical Practice (GCP). Compliance with GCP provides public assurance that the rights, safety, and well-being of study patients are protected consistent with the principles that have their origin in the Declaration of Helsinki.

8.1.1. Informed Consent and Medical Records Release Form

The Investigator will ensure that the patient is given full and adequate oral and written information about the nature, purpose, possible risk and benefit of the study. Patients must also be notified that they are free to discontinue from the study at any time. The patient should be given the opportunity to ask questions and allowed time to consider the information provided.

The Investigator will inform the patient/legal guardian if new information becomes available that may be relevant to the patient’s/legal guardian’s willingness to continue participation in the study. Communication of this information should be documented.

The patient’s signed and dated informed consent must be obtained before conducting any study tests or procedures that are not part of routine care.

The Investigator must maintain the original, signed ICF. A copy of the signed ICF must be given to the patient.

A medical records release form will be required of all patients for the purpose of obtaining vital status information from the patient’s physician or from death registries. The signing of this medical records release form is in addition to the ICF.

8.1.2. Ethical Review

The study protocol, including the ICF, must be approved or given a favorable opinion in writing by an IRB or IEC, as appropriate. The Investigator must submit written approval before he or she can enroll any patient into the study.

The Investigator is responsible for informing the IRB or IEC of any amendment to the protocol in accordance with local requirements. In addition, the IRB or IEC must approve all patient materials for the study (except those that support the need to remove an apparent immediate hazard to the patient). The protocol must be reapproved by the IRB or IEC upon receipt of amendments and annually, as local regulations require.

Initial IRB or IEC approval of the protocol, and all materials approved by the IRB or IEC for this study including the patient consent form and recruitment materials must be maintained by the Investigator and made available for inspection.

The Investigator will submit reports of SAEs as outlined in Section [6.5.7](#). In addition, the Investigator agrees to submit progress reports to the IRB or IEC per their local reporting requirements, or at least annually and at the conclusion of the study. The reports will be made available to the Sponsor or designee.

Any communications from regulatory agencies, IRBs, or IECs in regard to inspections, other studies that impact this protocol or the qualifications of study personnel should be promptly reported to the Sponsor or its designee.

The Investigator is also responsible for providing the IRB or IEC with reports of any reportable serious adverse drug reactions from any other study conducted with the study drug. The Sponsor or designee will provide this information to the Investigator.

Major changes in this research activity, except those to remove an apparent immediate hazard to the patient, must be reviewed and approved by the Sponsor and the IRB or IEC that approved the study. Amendments to the protocol must be submitted in writing to the Investigator's IRB or IEC and the Regulatory Authority for approval before patients are randomized under the amended protocol, and patients must be re-consented to the most current version of the ICF.

8.1.3. Serious Breach of Protocol

Investigators must notify the Medical Monitor within 24 hours of becoming aware of a potential serious breach of the protocol. A serious breach is a breach that is likely to affect to a significant degree the safety and rights of a study participant or the reliability and robustness of the data generated in the clinical trial.

8.1.4. Study Documentation, Confidentiality, and Records Retention

All documentation relating to the study should be retained for 2 years after the last approval in an ICH territory or as locally required, whichever is longer. If it becomes necessary for the Sponsor, the Sponsor's designee, applicable IRB/IEC, or applicable regulatory authorities to review or audit any documentation relating to the study, the Investigator must permit direct access to all source documents/data. Records will not be destroyed without informing the Sponsor in writing and giving the Sponsor the opportunity to store the records for a longer period of time at the Sponsor's expense.

The Investigator must ensure that the patients' confidentiality will be maintained. On the eCRFs or other documents submitted to the Sponsor or designees, patients should not be identified by their names, but by the assigned patient number or code. If patient names are included on copies of documents submitted to the Sponsor or designees, the names will be obliterated, and the assigned patient number added to the document. Documents not for submission to the Sponsor (eg, signed ICFs) should be maintained by the Investigator in strict confidence.

The Investigator must treat all of the information related to the study and the compiled data as confidential, whose use is for the purpose of conducting the study. The Sponsor must approve any transfer of information not directly involved in the study.

To comply with local and/or regional regulations, this clinical study may be registered, and study results may be posted on public registries, such as ClinicalTrials.gov.

8.1.5. End of Study

The end of study is defined as the last patient last visit.

8.1.6. Termination of the Clinical Study or Site Closure

The Sponsor, or designee, reserves the right to terminate the study or a clinical study site at any time. Conditions that may warrant this action may include, but are not limited to:

- The discovery of an unexpected, serious, or unacceptable risk to patients participating in the study
- Failure of the Investigator to comply with the protocol, the requirements of the IRB/IEC or local health authorities, the Sponsor's procedures, or GCP guidelines
- Inadequate recruitment of participants by the Investigator
- The decision on the part of the Sponsor to suspend or discontinue treatment with the study drug

Should the study be terminated, and/or the site closed for whatever reason, all documentation and study drug pertaining to the study must be returned to the Sponsor or its representative, and the Investigators, IRB/IEC and Regulatory Authorities will be promptly informed of the termination and the reason for the decision. The Investigator should promptly inform the patients and assure appropriate therapy and follow-up.

8.2. Data Quality Control and Quality Assurance

8.2.1. Data Handling

Study data must be recorded on CRFs (paper and/or electronic) provided by the Sponsor or designee on behalf of the Sponsor. CRFs must be completed only by persons designated by the Investigator. If eCRFs are used, study data must be entered by trained site personnel with access to a valid and secure eCRF system. All data entered into the eCRF must also be available in the source documents. Corrections on paper CRFs must be made so as to not obliterate the original data and must be initialed and dated by the person who made the correction.

8.2.2. Study Monitoring

The Monitor, as a representative of the Sponsor, has an obligation to closely follow the study conduct at the site. The Monitor will visit the Investigator and clinical study center periodically and will maintain frequent telephone and written contact. The Monitor will maintain current personal knowledge of the study through observation, review of study records and source documentation, and discussion of the conduct of the study with the Investigator and staff.

The Monitor will review source documents, systems and CRFs to ensure overall quality and completeness of the data and to confirm study procedures are complied with the requirements in the study protocol accurately. The Sponsor, or its designee, will be allowed to conduct site visits to the investigation facilities for the purpose of monitoring any aspect of the study. The Investigator agrees to allow the Monitor to inspect the drug storage area, study drug stocks, drug accountability records, patient charts and study source documents, site standard operating procedures and training records, and other records relative to study conduct.

8.2.3. Audits and Inspections

Periodically, the Sponsor or its authorized representatives audit clinical investigative sites as an independent review of core trial processes and documents to determine whether these activities were conducted, and data were recorded, analyzed, and accurately reported according to the protocol, GCP guidelines of the ICH, and any applicable regulatory requirements. A regulatory authority, an IEC or an IRB may visit the site to perform audits or inspections, including source data verification. The Investigator should contact the Sponsor and designee immediately if contacted by a regulatory agency, an IEC or an IRB about an inspection.

8.3. Publication Policy

It is intended that after completion of the study, the data are to be submitted for publication in a scientific journal and/or for reporting at a scientific meeting. A copy of any proposed publication (eg, manuscript, abstracts, oral/slide presentations, book chapters) based on this study, must be provided and confirmed received at the Sponsor at least 30 days before its submission. The Clinical Trial Agreement will detail the procedures for publications.

Authorship of any publications resulting from this study will be determined on the basis of the Uniform Requirement for Manuscripts Submitted to Biomedical Journals (International Committee of Medical Journal Editors).

10. APPENDICES

10.1. Polyneuropathy Disability (PND) Scores

Stage	Description
0	No symptoms
I	Sensory disturbances but preserved walking capability
II	Impaired walking capacity but ability to walk without a stick or crutches
IIIA	Walking with the help of one stick or crutch
IIIB	Walking with the help of two sticks or crutches
IV	Confined to a wheelchair or bedridden

10.2. New York Heart Association Class (NYHA)

Class	Symptomatology
I	No symptoms. Ordinary physical activity such as walking and climbing stairs does not cause fatigue or dyspnea.
II	Symptoms with ordinary physical activity. Walking or climbing stairs rapidly, walking uphill, walking or stair climbing after meals, in cold weather, in wind or when under emotional stress causes undue fatigue or dyspnea.
III	Symptoms with less than ordinary physical activity. Walking one to two blocks on the level and climbing more than one flight of stairs in normal conditions causes undue fatigue or dyspnea.
IV	Symptoms at rest. Inability to carry on any physical activity without fatigue or dyspnea.

10.3. Categorization of Infusion-Related Reactions

Signs and symptoms of an IRR usually develop during or shortly after drug infusion and generally resolve completely within 24 hours of completion of infusion. Signs/symptoms may include: allergic reaction/hypersensitivity (including drug fever), arthralgia (joint pain), bronchospasm, cough, dizziness, dyspnea (shortness of breath), fatigue (asthenia, lethargy, malaise), headache, hypertension, hypotension, myalgia (muscle pain), nausea, pruritus/itching,

rash/desquamation, rigors/chills, sweating (diaphoresis), tachycardia, urticaria (hives, welts, wheals), vomiting.

Categorization of IRRs is as follows:

Categorization	Description
Mild	Mild reaction: infusion may be continued; if intervention is indicated it is minimal and additional treatment (other than paracetamol for delayed reactions) is not required.
Moderate	Moderate reaction: requires treatment including more intensive therapy (eg, IV fluids, NSAIDs) in addition to infusion interruption but responds promptly to medication. Treatment is indicated for ≤ 24 hours.
Severe	More than moderate reaction: not rapidly responsive to medication or to interruption of infusion; and/ or prolonged (treatment is indicated for >24 hours); recurrence of severe symptoms following initial improvement.

**ALN-TTR02-011 PROTOCOL AMENDMENT 3
SUMMARY OF CHANGES DATED 30 JUNE 2021**

**APOLLO-B: A Phase 3, Randomized, Double blind, Placebo-controlled Multicenter Study
to Evaluate the Efficacy and Safety of Patisiran in Patients with Transthyretin Amyloidosis
with Cardiomyopathy (ATTR Amyloidosis with Cardiomyopathy)**

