5.2.4. Suggested Guidelines for Management of Infusion-related Reactions

Criteria for categorizing IRRs are provided in Section 10.3.

- In the event of an IRR, the infusion of study drug may be slowed or stopped and the patient closely monitored until resolution of the reaction. Drugs that may be used to facilitate resolution and permit resumption of study drug administration include but are not limited to: paracetamol/acetaminophen (or equivalent), additional histamine H1/H2 receptor antagonists (eg, ranitidine), nonsteroidal anti-inflammatory drugs (NSAIDs), adrenaline, supplemental oxygen, IV fluids, and/or corticosteroids.
- Following resolution of a mild or moderate IRR that required interruption of the study drug infusion, resumption of administration may occur at the Investigator's discretion at a slower infusion rate for that dose and for subsequent doses of study drug. If the infusion is delayed, the administration of the infusion should be completed no more than 16 hours after study drug is first diluted in saline (including infusion time).

- Study drug administration will not be resumed for any patient following a severe IRR until the case is discussed with the Medical Monitor.
- If after consultation with the Medical Monitor it is agreed that an individual patient's steroid premedication will be increased, then the following steps are **recommended**:
 1. If the IRR occurred while the patient received 10 mg IV dexamethasone or equivalent at least 60 minutes before the infusion and did not resolve with slowing of the infusion rate, then the patient should be increased by multiples of 5 mg IV dexamethasone or equivalent at least 60 minutes before the infusion.
 2. Increased dose of premedication steroids should NOT exceed the combination of 20 mg IV dexamethasone or equivalent on the day of infusion.
 3. If the IRR occurred while the patient received less than 10 mg IV dexamethasone or equivalent, then the patient should return to the prior dose of IV dexamethasone or equivalent that did not result in an IRR.

Patients will be instructed to call the Investigator if they experience symptoms such as fever, chills, myalgia, or nausea/vomiting after discharge from the site.

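### The Severe row of the infusion-reaction scale (Protocol 10.3) has no life-threat or urgent-intervention criterion, so a promptly resolving anaphylactic-type reaction can be read as Moderate and the infusion resumed the same day without Medical Monitor discussion

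*Protocol*

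**What the plan says.** Section 10.3 of the protocol describes what an IRR may look like and sorts IRRs into Mild, Moderate and Severe. The signs include some that also occur in anaphylaxis: "Signs/symptoms may include: allergic reaction/hypersensitivity (including drug fever), arthralgia (joint pain), bronchospasm", with hypotension and urticaria later in the same list.

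A Moderate reaction is one that "requires treatment including more intensive therapy (eg, IV fluids, NSAIDs) in addition to infusion interruption but responds promptly to medication", with treatment needed for no more than 24 hours. A Severe reaction is "More than moderate reaction: not rapidly responsive to medication or to interruption of infusion; and/ or prolonged (treatment is indicated for >24 hours"), or "recurrence of severe symptoms following initial improvement".

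Section 5.2.4 uses this scale to decide on restarting: "Criteria for categorizing IRRs are provided in Section 10.3". For the lower grades, "Following resolution of a mild or moderate IRR that required interruption of the study drug infusion, resumption of administration may occur". The decision is left to the Investigator, and a reduced rate is then used for that dose and for later ones. After a severe IRR, study drug may not be resumed until the case has been discussed with the Medical Monitor. The same section introduces a list of rescue measures with "Drugs that may be used to facilitate resolution and permit resumption of study drug administration include but are not limited to"; the list includes "adrenaline, supplemental oxygen, IV fluids, and/or corticosteroids" and is not tied to any grade.

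Section 6.5.7.2 records every IRR as an adverse event. Section 6.5.7.1 grades an adverse event Severe if, among other things, it has life-threatening consequences or calls for urgent intervention.

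**The concern.** The grade under 10.3 determines whether a second opinion is mandatory before the drip is restarted. The stated Severe criteria concern how quickly the reaction responds, how long treatment is needed, and whether severe symptoms come back. How dangerous the reaction was at its worst is not among them. A reaction that is alarming but responds quickly to treatment could therefore fall into the category that needs no discussion before restart.

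At stake is re-exposure of a patient, within hours, to the product that has just caused a serious hypersensitivity reaction. Section 1.6 names severe hypersensitivity as an important potential risk and states that patisiran is contraindicated in patients with such a history. The patients here have heart failure and may be up to 85 years old, and some infusions may be given at home by a healthcare professional after at least two uneventful doses at the centre.

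**Working it through.** There is no figure to reproduce. The check is to take one case through the relevant sections.

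**Test case.** Bronchospasm and hypotension during the infusion; the infusion is interrupted; adrenaline and IV fluids are given; the reaction settles promptly; treatment is needed for less than 24 hours; nothing recurs.

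**Step 1: grade under 10.3.**

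| Stated criterion | Test case |
|---|---|
| Moderate: more intensive therapy plus interruption | met |
| Moderate: prompt response to medication | met |
| Moderate: treatment for 24 hours or less | met |
| Severe: not rapidly responsive | not met |
| Severe: treatment beyond 24 hours | not met |
| Severe: recurrence of severe symptoms | not met |

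The case meets 3 of 3 stated Moderate criteria and 0 of 3 stated Severe criteria. Of the three Severe criteria, 0 refer to threat to life or urgency of intervention. The lead-in to the Severe row (a reaction that is more than moderate) leaves room for judgement but does not say what to judge by.

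**Step 2: consequence under 5.2.4.** Read as Moderate, the infusion may be resumed at the Investigator's discretion. Read as Severe, it may not be resumed before discussion with the Medical Monitor.

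**Step 3: grade under 6.5.7.1.** If the event was life-threatening or needed urgent intervention, it is Severe as an adverse event, however fast it resolved. The two scales can then give different grades for one event, and 5.2.4 points to 10.3.

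**Step 4: do other provisions intervene in time?**

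- *SAE reporting.* A life-threatening event is an SAE, and 6.5.7.1 gives intensively treated allergic bronchospasm as an example of an important medical event. Section 6.5.7.4 requires the report within 24 hours of the site learning of the event. Doses are 3 weeks apart (plus or minus 3 days), so the report is due at least 21 − 3 − 1 = 17 days before the next in-window dose if that dose follows an on-schedule one. If the current dose was itself late in its window and the next is early, the gap between doses is 21 − 6 = 15 days and the margin is 14 days. A dose delayed to the 7-day limit, followed by one 3 days early, gives 21 − 10 = 11 days and a margin of 10 days. The Sponsor should therefore know before any later dose. For the interrupted infusion the order can be reversed: 5.2.4 allows a delayed infusion to be completed up to 16 hours after dilution, and 16 is less than 24.
- *Section 5.2.5.* The Medical Monitor should be contacted, and the dose may be held, if the Investigator judges that a drug-related event makes further dosing a potential risk. This depends on the Investigator's judgement and is not a required step before restart.
- *Section 1.6 and exclusion criterion 26.* The contraindication stands in the benefit-risk text, and the exclusion criterion works at entry. Section 5.2.4 does not apply either to a reaction that occurs on study.
- *Section 4.3.1.* An adverse event is listed as a reason for discontinuing study drug, with no specific rule for hypersensitivity.

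**Result.** Later doses are largely covered. A same-day restart of the interrupted infusion is not covered by any required discussion if the event is read as Moderate.

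**The case against.** The best case against the point has several parts.

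- *The Moderate reading is not forced.* The Severe row opens with a general phrase, its recurrence clause presupposes that symptoms can be judged severe, and the Moderate examples are IV fluids and NSAIDs, not adrenaline. This stands. A careful Investigator could grade the test case Severe, and a reader who infers that the protocol requires a Moderate grade goes further than the text.
- *The rescue list proves nothing about grade.* It may seem that naming adrenaline among drugs that can permit resumption shows adrenaline-treated reactions to be Moderate. The list applies to any IRR, and Severe IRRs may also be resumed after discussion, so that inference fails.
- *Later doses are protected.* A reader might infer that the patient can be re-dosed for months with nobody else aware. SAE reporting within 24 hours against a 3-week dosing interval answers most of that. It is notification and not a mandated discussion before dosing, but it confines the concern mainly to the same day.
- *Two scales are not a contradiction.* One guides infusion management and the other grades adverse events. That is fair. The point is only that the restart rule uses the scale without a life-threat criterion. Nor does 5.2.4 contradict the contraindication in 1.6, since it is headed as suggested guidance and says that resumption may occur.
- *Detail may lie elsewhere.* Section 5.2.1 refers to the Pharmacy Manual for further detail on IRR management, and Section 1.6 to the Investigator's Brochure. Neither is shown, and an anaphylaxis rule could be in either. This limits confidence, although the protocol's own grading table would still lack the criterion.

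**Conclusion.** The point holds in a limited form. The Severe row of 10.3 states no life-threat or urgent-intervention criterion, so a promptly resolving anaphylactic-type reaction can be read as Moderate, and the interrupted infusion could then be resumed the same day at the Investigator's discretion without the discussion required after a Severe IRR. The documents do not support saying that this grade is compelled, that later doses go unprotected, or that sections contradict each other.

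Severity is low, and this is best labelled a cheap improvement. The protocol gives no anaphylaxis rate, so the frequency cannot be quantified; Section 1.6 reports that in the earlier Phase 3 study and its ongoing extension all IRRs were mild or moderate and none was an SAE. Section 1.3.1 reports IRRs of any grade in 19% of patisiran and 9% of placebo patients in the earlier Phase 3 study. That suggests the scale will be used often, but it says nothing about how often the gap would matter. The conclusion assumes that the Pharmacy Manual does not already contain an explicit stopping rule for anaphylaxis.

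**What to change.** Two short changes:

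1. In the Severe row of 10.3 add: *or life-threatening consequences or urgent intervention indicated (eg, anaphylaxis), regardless of speed of response*. This aligns the row with 6.5.7.1.
2. In 5.2.4 state that study drug is not resumed after on-study anaphylaxis or other severe hypersensitivity. This carries the contraindication in 1.6 into the operational text.

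The Pharmacy Manual should be checked for matching wording. The cost is a few more calls to the Medical Monitor and rare discontinuations of study drug; no endpoint, sample size or visit schedule changes.
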